### 7.4.2 Final Analysis

The final analysis of the study will be completed no later than after 50 subjects have completed both Treatment (Arm A) and Control (Arm B) of the study. However, the Sponsor may determine according to interim analysis results that both safety and efficacy endpoints have been achieved for the Phase IIb study. The Sponsor can make this determination at any time following the first interim analysis timepoint.

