This protocol is designed to evaluate the clinical outcomes following intramyocardial delivery of autologous UCB-MNC and is being conducted to investigate this product and its delivery procedure as a potential new therapy to strengthen the right ventricle of patients with HLHS or HLHS variants. The central hypothesis of this study is that the delivery of the autologous UCB-MNC product into the myocardium of the right ventricle of the heart at the time of Stage II surgical repair will provide a short-term improvement in cardiac function, reaching growth and developmental milestones, and quality of life, while also providing a reduction in the cumulative days of hospitalization following discharge for the Stage II surgical repair. It is also hypothesized that the autologous UCB-MNC product and its delivery procedure will ultimately provide long-term improvement in cardiac function, reaching growth and developmental milestones, reaching Stage III surgical repair pre-operative work-up, prolonging time to cardiac transplantation or death, and improving quality of life.

The safety and efficacy endpoints will be evaluated by the DSMB at least annually. This will determine the appropriateness of continued enrollment in both arms of this Phase IIb study. By demonstrating reasonable efficacy and safety of this product and its delivery procedure in this study, future definitive studies may be designed with the goal to establish a marketable regenerative therapy to treat this rare, life-threatening congenital heart disease as quickly as possible.

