## 2 STUDY OBJECTIVES

The purpose of this Phase IIb clinical study is to evaluate the efficacy and safety of autologous UCB-MNC intramyocardial injections into the single, morphological right ventricle of subjects with HLHS or HLHS variants requiring Stage II surgical repair. Thirty to fifty treated subjects and thirty to fifty control subjects will be accrued. Subjects accrued in the treatment arm (Arm A) of this study will be treated with a single dose following successful completion of Stage II surgical repair. Subjects accrued in the control arm (Arm B) of this study will be followed according to the same protocol requirements as the treatment arm but will not receive cell therapy. In the treatment and control arms, surrogate markers of cardiac function, growth, success in reaching Stage III surgical repair pre-operative work-up, time to cardiac transplantation or death, and cumulative days of hospitalization will be recorded and evaluated following the completion of Stage II surgery for up to four years, or until the pre-operative work-up for the Stage III surgical repair has been completed or until cardiac transplant, whichever is first. Development and quality of life as measured by questionnaires will also be monitored. Follow-up surrogate markers and the other variables noted above that are recorded for this study will be compared to baseline and by study arm. The surrogate markers and other variables are described in Section 3 of this protocol.

The objective is to evaluate the short-term (up through 3 months post-Stage II surgical repair) cardiac function, growth, and cumulative days of hospitalization following discharge for the Stage II surgical repair in the treatment and control arms, adjusting for baseline.

This evaluation will also include long-term (6 months and up to 4 years post-Stage II surgical repair or until the pre-operative work-up for the Stage III surgical repair has been completed or until cardiac transplant), cardiac function, growth, ability to reach Stage III surgical repair pre-operative work-up and time to cardiac transplantation or death in the treatment and control arms, adjusting for baseline.

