### 7.1 Sample Size Determination

Sample size calculations were performed using alpha = 0.05 and assume equal variance across study arms. With 50 subjects per arm we will have 80% power to detect an effect size as small as 0.57 in difference in cardiac function measures. This is built on the assumption all subjects from both arms have complete data at baseline and 3-month follow-up visits. In the event of attrition or incomplete data in 40% of participants, equal across study arms, the study has 80% power to detect an effect size as small as 0.74 in difference in cardiac function measures.

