#### Multiplicity

For both the primary analyses of short-term outcomes and the secondary analysis of long-term analyses, there will be one primary (or first) analysis and thus no correction will be made for multiple comparisons. A sequence of outcomes of interest is also given (Sections 3.2 and 3.3) for each of the short and long-term outcomes, and significance will be assessed in the order of these sequences. Therefore, no adjustment is made for multiple testing.

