## 7.4 Analysis

### 7.4.1 Interim Analysis

This study has 5 planned safety and efficacy interim analysis planned. An interim analysis will be performed according to statistical analysis plan on all enrolled subjects after 10, 20, 30, 40 and 50 subjects have been treated and completed the 3-month follow-up visit. Results will be reviewed by the DSMB.

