### 7.4.3 Short Term Efficacy Analysis

#### Primary Outcome

The primary analysis of the primary outcome apical fractional area change 3 months post Stage II palliative surgery will be done using analysis of covariance (ANCOVA), including a model term for the difference in means between the cell-based therapy and control groups, as well as a model term for apical fractional area change at time of surgery to account for subject baseline condition. In secondary analyses of the primary outcome we will, using interaction terms, fit a model allowing the treatment effect (mean difference between the cell-therapy and control groups) to depend on baseline fractional area change.

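### Five efficacy looks, with the Sponsor free to declare the efficacy endpoints achieved after the first, have no criterion, boundary or alpha spending, so the error rate of an early claim is uncontrolled

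*Combined protocol and SAP*

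**What the plan says.** Section 7.4.1 schedules five interim analyses, labelled as covering safety and efficacy, "on all enrolled subjects after 10, 20, 30, 40 and 50 subjects have been treated and completed the 3-month follow-up visit". Only treated subjects trigger a look; the number of controls at each look is not given. Results go to the DSMB.

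Section 7.4.2 places the final analysis no later than 50 per arm. It adds that the Sponsor may determine from interim results that both safety and efficacy endpoints have been met: "The Sponsor can make this determination at any time following the first interim analysis timepoint".

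The other relevant places are:

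- **Section 7.1:** "Sample size calculations were performed using alpha = 0.05 and assume equal variance across study arms". Power is 80% for an effect size of 0.57 with 50 per arm, and for 0.74 if 40% of data are missing.
- **Section 7.3, Multiplicity:** for the short-term and for the long-term outcomes, "there will be one primary (or first) analysis and thus no correction will be made for multiple comparisons". The second argument is that outcomes are tested in a fixed order.
- **Section 7.4.3:** the model is an ANCOVA; it names "The primary analysis of the primary outcome apical fractional area change 3 months post Stage II palliative surgery". Section 3.2 defines the same primary endpoint by FAC, circumferential strain and longitudinal strain.
- **Section 2:** "Thirty to fifty treated subjects and thirty to fifty control subjects will be accrued".
- **Section 8.11:** the stopping rules concern safety only.
- **Section 8.13:** the DSMB is advisory.
- **Section 1:** "The safety and efficacy endpoints will be evaluated by the DSMB at least annually".

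**The concern.** Sections 7.4.1 and 7.4.2 together allow an efficacy claim at several points, the earliest with 10 treated subjects, and leave the criterion to the party that benefits from the claim. Section 7.4.1 refers to the statistical analysis plan for method, but Section 7, which carries that title, gives no per-look level, boundary or rule for *achieved*. The reasoning in 7.3 covers several outcomes tested once; it does not cover one outcome tested several times.

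Two things are at stake. The 0.05 level behind the sample size and the significance statements does not govern an early claim. And a claim made at a small look tends to overstate the effect carried into the definitive studies that Section 1 foresees. A declaration at 10 or 20 treated is also not reconciled with the stated 30 to 50 per arm.

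**Working it through.** **1. Reproduce Section 7.1.** For a two-sample comparison with n per arm, the detectable standardised effect is roughly (1.96 + 0.84) × √(2/n).

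- n = 50: 2.80 × 0.200 = 0.56. The exact t-test gives 0.566 (stated 0.57).
- n = 30 (50 less 40%): 2.80 × 0.258 = 0.72. The exact t-test gives 0.736 (stated 0.74).
- A one-sided 0.05 test at n = 50 would give 0.50.

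The plan's figures are therefore those of one two-sided test at 0.05, that is, 2.5% in the direction favouring cells.

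**2. Repeated looks, no true effect.** The assumptions are mine, not the plan's: *achieved* means two-sided p<0.05 on 3-month FAC alone, arms are equal at each look, and the look at 50 is the final analysis. Test statistics at looks j<k have correlation √(n_j/n_k). The chance of at least one crossing came from numerical integration and from simulation of t-tests and of ANCOVA (assumed baseline correlation 0.5).

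| Looks per arm | Favouring cells | Either direction |
|---|---|---|
| 50 only | 2.5% | 5% |
| 30, 40, 50 | 4.6% | 9.1–9.3% |
| 10, 20, 30, 40, 50 | 7.1–7.3% | 14.2–14.6% |

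Over the five looks the t-test rate favouring cells accumulates as about 2.4, 4.2, 5.4, 6.4 and 7.2%.

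**3. Vary the assumptions (five looks, favouring cells).**

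- Controls lag (assumed 3/8/15/25/50 at the five looks): 8.2%. Controls lead (20/30/40/50/50): 6.8%.
- FAC and both strains must all be significant, assumed correlations 0.3 to 0.8: about 0.2–2.3%, below nominal.
- Any one of the three suffices, same correlations: about 13–18%.

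**4. Exaggeration.** At look n, significance needs an observed difference of at least t × √(2/n) SD.

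- n = 10: 2.10 × 0.447 = 0.94
- n = 30: 2.00 × 0.258 = 0.52
- n = 50: 1.98 × 0.200 = 0.40

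Mean estimate at a claim favouring cells, when the true effect is 0.57 SD:

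| Rule | Mean estimate (SD) |
|---|---|
| One significant test at 50 per arm | 0.64 |
| p<0.05 at 30/40/50 | 0.67 |
| p<0.05 at all five looks | 0.78 (1.13 for claims at the first look) |
| Lan-DeMets limits at 30/40/50 | 0.69 (0.86 for claims at the look at 30) |

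**5. A boundary.** O'Brien-Fleming-type spending per tail is α(t) = 2[1 − Φ(2.241/√t)], with t the share of full information. For 30/40/50 of 50, t = 0.6, 0.8 and 1, which spends 0.0038, 0.0122 and 0.025 cumulatively. The limits are z = 2.669, 2.289 and 2.031, or two-sided p of about 0.0076, 0.022 and 0.042. Simulated null error is then 2.5% favouring cells. Power at 0.57 is 79.6%, against 80.6% for one look.

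**The case against.** The strongest reply is that p<0.05 at each look is not in the plan, so 7.2% is not a property of the plan. That is right. A reader might infer that the trial has a false-positive rate of 7.2%, or 14% in both directions, but the documents do not support this. Section 7.4.2 speaks of endpoints in the plural and Section 3.2 names three measures, so a strict reading could fall below 2.5% and a loose one could be far above 7.2%. What stands is that the plan gives no basis for any figure, and this is the defect.

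Second, 30 per arm may be meant as a floor. Section 2 supports that reading and the wording of 7.4.2 contradicts it, so both are open. Even with the floor, the FAC-only rate is 4.6%.

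Third, a reader might blame the early looks for all the over-estimation. Most of it does not come from them if claims start at 30 per arm: one significant final test already averages 0.64 SD, and unadjusted looks from 30 add about 0.03. The larger distortion comes from claims at 10 or 20 per arm.

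Fourth, a reader might count the annual DSMB reviews as further efficacy looks. Section 1 points that way, but the tables listed in 8.13 name no efficacy comparison, although the DSMB may request other information. This is an ambiguity, not a finding.

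Finally, the study is open-label, non-randomised and Phase IIb, so error control would not make its claim confirmatory. That is true, but the plan itself sets an alpha, a power and an order of testing, and the early declaration escapes all three.

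**Conclusion.** The concern holds: the early efficacy declaration allowed by 7.4.2 has no criterion, no boundary and no alpha spending, and neither 7.3 nor 7.1 covers it. Its error rate is uncontrolled, rather than known to be a particular value.

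In the FAC-only illustration with p<0.05 at each look, equal arms and the look at 50 as final, a false claim favouring cells is about 7.2% over five looks or 4.6% from 30 per arm, against 2.5%. Uneven control accrual moves the five-look figure to about 6.8–8.2%. The undefined criterion matters more: about 0.2–2.3% if all three measures must be significant, and 13–18% if any one suffices. The safety condition in 7.4.2 is not modelled and could only lower these rates. Bias from non-random assignment is outside the calculation.

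This should be settled before any interim efficacy comparison is seen, because a criterion chosen afterwards would not be credible.

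**What to change.** Amend 7.4.1 and 7.4.2 in one of two ways.

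**(a) Preferred.** Make every look before one named final analysis safety-only, with no efficacy declaration before it. Power is unchanged.

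**(b) Alternative.**

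- Define *achieved* as the 3-month FAC ANCOVA of 7.4.3 crossing an O'Brien-Fleming-type Lan-DeMets limit (0.025 per tail) in favour of cells.
- Allow no declaration before 30 per arm have 3-month FAC.
- Compute limits from the information observed in both arms. With complete data at 30/40/50 the p limits are about 0.0076, 0.022 and 0.042.
- Spend all remaining alpha at one named final analysis, only if accrual did not end because of interim efficacy results. If any look could be made final on its result, the error favouring cells returns to about 4.4%.
- To make that condition workable, keep comparative interim efficacy results with the DSMB and tell the Sponsor only whether the limit was crossed.
- Attach a stopping-adjusted estimate to any early claim, since (b) does not remove over-estimation.

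Option (b) costs about one point of power at 0.57 (80.6% to 79.6%). In the plan's own case, "In the event of attrition or incomplete data in 40% of participants, equal across study arms, the study has 80% power", 30 per arm have data, so the final test is the only efficacy test. It stays at p<0.05, with power 80.5% at 0.74; holding it at 0.0076 would leave 54.3%. If accrual ends at 40 per arm for unrelated reasons after a look at 30, the final limit is about 0.049 and power at 0.57 is 71.0%, against 71.1% for one look.

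Under either option, add repeated looks to 7.3 and state whether the annual DSMB reviews include the efficacy comparison. Restate power in 7.1 if (b) is chosen. No patients are added; the Sponsor gives up the discretion to claim efficacy early. Confounding from non-random assignment needs separate treatment.

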### 7.4.3 Short Term Efficacy Analysis

#### Primary Outcome

The primary analysis of the primary outcome apical fractional area change 3 months post Stage II palliative surgery will be done using analysis of covariance (ANCOVA), including a model term for the difference in means between the cell-based therapy and control groups, as well as a model term for apical fractional area change at time of surgery to account for subject baseline condition. In secondary analyses of the primary outcome we will, using interaction terms, fit a model allowing the treatment effect (mean difference between the cell-therapy and control groups) to depend on baseline fractional area change.

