Reference therapy	Control cohort of 30-50 subjects, enrolled in the control arm of this study, not receiving the cell product, which will be enrolled and followed using the inclusion/exclusion criteria and follow-up requirements outlined herein.
Treatment Assignment	When possible, prior to enrollment in this study, expecting parent(s) with the prenatal diagnosis of HLHS or HLHS variants will be offered enrollment in a separate protocol for the collection of UCB. The collected UCB will be used for UCB-MNC treatment described herein if the subject is enrolled in and meets all eligibility criteria for this open-label study, and if the UCB-MNC manufactured product is determined to be acceptable for release to the investigational site for clinical use. Subjects without frozen UCB-MNC product available or with frozen UCB-MNC that is NOT acceptable for clinical use, or that choose not to participate in the treatment arm may be enrolled in the control arm of this study.
Primary and Secondary Short-Term Endpoints	
The primary short-term efficacy endpoint regarding the cell product and its delivery procedure is:
 
Change in right ventricular cardiac function at 3 months post-Stage II surgery compared to baseline, measured by apical fractional area change (FAC), circumferential strain, and longitudinal strain all as determined by echocardiography.
 
Secondary short-term safety and efficacy outcomes in order of their relevance and importance in this clinical study are:
 
 
1) Change in right ventricular cardiac function between baseline and hospital discharge for Stage II surgery, measured by echocardiogram.
 
2) Cumulative days of hospitalization per patient at 1 and 3-months post Stage II surgery.
 
3) Change in weight, heart rate, and oxygen saturation at 3-months post Stage II surgery compared to baseline.
 

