Primary and Secondary Long-Term Endpoints	
The primary long-term efficacy endpoint regarding the cell product and its delivery procedure is:
 
Change in right ventricular cardiac function at 12 months post-Stage II surgery compared to baseline, measured by echocardiogram.
 
Secondary long-term safety and efficacy endpoints in their order of relevance and importance in this clinical study are:
 
 
1) Change in weight every 6 months post-Stage II surgery compared to baseline.
 
2) Change in heart failure medication taken every 6 months post-Stage II surgery compared to baseline.
 
3) Change in arrhythmia medication taken every 6 months post-Stage II surgery compared to baseline.
 
4) Success of subject being scheduled for Stage III surgical repair.
 
5) Time (days) until listed for cardiac transplantation, or death following the 6-month follow-up.
 
6) Change in right ventricular function at Stage III surgery pre-op work-up compared to baseline, obtained by echocardiogram and cardiac catheterization.
 

Statistical Methodology	
Quantitative outcomes, like FAC, at specified time post-surgery, will be analyzed using analysis of covariance to estimate the difference in means between the cell-based therapy and control groups after adjusting for the baseline value (the measured value of the same variable, e.g. FAC, at the time of Stage II surgery). Categorical outcomes, like able to undergo Stage III palliation surgery, will be compared between groups using a chi-square test. Time-to event outcomes, like time until listing for cardiac transplant, will be compared using the Kaplan-Meier method and log-rank test. We will similarly do analyses of other variables based upon this patient subset. In secondary analyses we will also fit models which allow the treatment effect (mean difference between the cell-therapy group control groups) to depend on baseline cardiac function measures or other baseline values. This will be done by using the linear, logistic and Cox regression models as appropriate.

Imaging Core Lab	
M. [name] (Core Lab Director) Mayo Clinic Pediatric and Adolescent Medicine [name] [name]

Contract Manufacturing Organization	
ReGen Theranostics, Inc. [name] [name]

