## 1 INTRODUCTION

This document is a protocol for a human research study involving subjects who require surgical palliation for HLHS and HLHS variants. This study aims to deliver an autologous cell-based product at the time of planned Stage II surgery and will be carried out in accordance with the applicable FDA regulations and this protocol. Based on the safety data from the initial 10 treated subjects in our Phase I safety study, we herein propose this Phase IIb efficacy study using autologous UCB as the source for MNC that will be delivered into the myocardium of the right ventricle. The objective of this study is to evaluate the short and long-term surrogate markers of safety and efficacy of autologous UCB-MNC intramyocardial injections. This add-on procedure is anticipated to pose little risk to the subject and has the potential to foster a new strategy that leverages the regenerative capacity of the pediatric heart during clinically mandated, multi-stage surgical repair.

This study will not be randomized as our preliminary data (summarized in 1.4) suggests that cell-based therapy may be beneficial to this high-risk patient population with little evidence to indicate there are any measurable safety concerns. This safety and efficacy data are consistent with our ongoing pre-clinical studies that are conducted using a double-blinded, randomized study design. Previously collected autologous umbilical cord blood in the UCB Collection Study will be used in the treatment arm of this open-label study. Controls will be screened using identical clinical inclusion/exclusion criteria that either do not have UCB collected as part of the UCB Collection Study, UCB-MNC product that is determined to be unacceptable for investigational use, or that choose to not participate in the treatment arm of this study.

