The feasibility of the Phase I study was most significantly compromised by the study inclusion and exclusion criteria. One in every six acceptable autologous products was administered during the Stage II surgery based largely on the narrow Phase I study eligibility criteria. The Phase IIb study has been designed to address the feasibility issue identified in Phase I by requiring fewer exclusion criteria for subject enrollment. It is anticipated that one out of every two subjects with manufactured autologous product will be eligible for enrollment in the treatment arm of this Phase IIb study. Therefore, treating up to fifty subjects under this Phase IIb study should be feasible within a 5-7 site clinical trial.

The feasibility of the Observational study that required prospective data collection for control subjects proved to be highly problematic as recruitment was limited to only three subjects in this time period. The primary limitation to recruitment was in part the bias for eligible subjects to choose to participate in the treatment study. Only a few subjects that met all eligibility criteria and had available UCB product decided to not participate in the Phase I cell-delivery study. Additionally, a significant number of subjects that did not have available autologous product and met all eligibility criteria of the Observational study were unwilling to participate in the Observational study that required multiple non-standard of care clinical visits with additional blood and imaging studies. Therefore, the Phase IIb study was designed with fewer non-standard of care clinical visits to address the feasibility of recruiting a proper control cohort.

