## 3 STUDY DESIGN

### 3.1 General Design

This Phase IIb study is a multicenter, prospective, open-label, non-randomized, observational study designed to evaluate the efficacy and safety of UCB-MNC delivered into the right ventricular myocardium of subjects with HLHS or HLHS variants with right ventricular dependent single ventricular CHD at the time of a planned Stage II surgical repair. This will be achieved by comparing the data collected in the treatment group (Arm A) to the equivalent data collected in the control group (Arm B), adjusting for baseline.

The concurrent control arm (Arm B) must meet identical study eligibility criteria as the treatment arm (Arm A), except for the requirements related to UCB-MNC product acceptability and DMSO sensitivity. The control arm will undergo the same planned Stage II surgical repair without the investigational cell delivery add-on procedure and will follow-up post-surgery in the same manner as the treatment arm (see Section 6 of this protocol).

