### 4.2 Consent/Screening

Potential subjects for the treatment arm (Arm A) of this study will be pre-screened from the Umbilical Cord Blood collection study. Parent(s) and/or legal guardian(s) of a child with HLHS or HLHS variant with single right ventricular dependent CHD requiring Stage II surgical repair, whose UCB-MNC has been documented to be acceptable for release to the investigational site, and whose child appears to meet the other study eligibility criteria (Section 4.1) during pre-screening may be consented to allow their child to participate in the treatment arm of this study.

Potential subjects for the control arm (Arm B) will be pre-screened during cardiology visits when Stage II surgery is being scheduled at the investigational site. Otherwise, potential subjects for the control arm will be pre-screened from the Umbilical Cord Blood collection study when their product is documented to not be acceptable for release to the investigational site. Parent(s) and/or legal guardian(s) of a child with HLHS or HLHS variant with single right ventricular dependent single ventricular CHD requiring Stage II palliative reconstructive surgery and whose child appears to meet all other study eligibility criteria (Section 4.1) during pre-screening may be consented to allow their child to participate in the control arm of this study.

Consent will occur after the parent(s) and/or legal guardian(s) have discussed the study with the study staff, a site investigator has pre-screened subject eligibility, and the parent(s) and/or legal guardian(s) have been provided adequate time and information to decide if they would like their child to participate. If both parent(s) and/or legal guardian(s) do not sign informed consent, the reason for only one parent or legal guardian signing should be documented at the time of informed consent. Consent must occur before any study procedures are completed, however standard of care procedures done within 30 days prior to Stage II surgery may be used rather than repeating procedures to collect study data. The original signed informed consent will be filed in the subject file and a copy will be given to the parent(s) and/or legal guardian(s). The informed consent process will be documented and provided in the subject file.

All subjects will enter screening phase at the time of informed consent.

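### The primary ANCOVA of this non-randomised comparison adjusts for no covariate beyond baseline FAC, so prognostic differences that baseline FAC does not capture would be read as treatment effect

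*Combined protocol and SAP*

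**What the plan says.** Section 3.1 calls this a "multicenter, prospective, open-label, non-randomized, observational study".

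**How children reach each arm**
- Arm A requires earlier cord-blood collection and an acceptable product (Section 4.1.1).
- Arm B takes children with no product or an unacceptable one (Section 3.1.1). It also takes those "or that choose not to participate in the treatment arm may be enrolled in the control arm of this study" (Clinical Study Summary; the Introduction agrees: "or that choose to not participate in the treatment arm of this study").
- The recruitment routes differ. Arm A is pre-screened from the cord-blood collection study. For the other arm, Section 4.2 says "Potential subjects for the control arm (Arm B) will be pre-screened during cardiology visits when Stage II surgery is being scheduled", or else through the collection study once a product is found unacceptable.
- Section 1.4 says that failures to obtain a product arose mostly because the mother delivered early or consented late.
- Section 1.4 also says of the earlier observational control study: "The primary limitation to recruitment was in part the bias for eligible subjects to choose to participate in the treatment study". It adds that only a few eligible families with a product declined treatment.

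**How the arms are compared**
- The primary model in Section 7.4.3 has an arm term "as well as a model term for apical fractional area change at time of surgery to account for subject baseline condition". The other short-term outcomes are handled similarly, and Section 7.4.4 repeats the model for 12-month FAC.
- The Clinical Study Summary adds secondary models that allow the treatment effect "to depend on baseline cardiac function measures or other baseline values". The other values are not named.
- Section 7.4.6 fits hospital effects as a further analysis, for at least the primary and first secondary endpoints.
- Section 7.3 describes baseline by arm. It plans no covariate-based control of confounding.

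**The concern.** In a randomised trial, an ANCOVA on arm and baseline gives an unbiased comparison, and any further covariate only buys precision. Here the covariates also have to make the arms comparable, and the plan asks baseline FAC to do that alone.

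Two statements in the protocol make this doubtful. First, early delivery is a documented route to having no product, and so to Arm B; it could plausibly affect outcome by paths other than FAC before Stage II. Second, Section 1.1 says routine echocardiography does not detect early dysfunction in the single right ventricle, so an echo measure may miss part of a child's starting condition.

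At stake is the meaning of the primary estimate and its p-value. If the arms differ in something prognostic that FAC misses, neither can separate that difference from the effect of the cells, and a larger sample does not shrink the bias. Section 7.4.2 lets the sponsor decide at any time after the first interim that the endpoints have been achieved, so the model matters at every look.

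**Working it through.** **1. The plan's own figures.** Section 7.1 gives detectable effects of 0.57 SD at 50 per arm, and 0.74 SD after 40% attrition (50 × 0.6 = 30 per arm), at alpha 0.05 and 80% power. A two-sided two-sample t test gives 0.566 and 0.736, so both reproduce. They assume an unbiased comparison and no baseline adjustment.

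**2. The two-term ANCOVA.** Let ρ be the correlation of baseline with 3-month FAC; 0.6 is assumed, as the documents give none. In SD units, SE = √(2/n) × √(1 − ρ²) = 0.8 × √(2/n).

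| n per arm | SE | t critical (df) | Effect detectable at 80% power | t × SE | Bias that removes significance |
|---|---|---|---|---|---|
| 50 | 0.160 | 1.985 (97) | 0.453 | 0.318 | 0.453 − 0.318 = 0.135 |
| 30 | 0.207 | 2.002 (57) | 0.589 | 0.414 | 0.589 − 0.414 = 0.175 |

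The last column takes an estimate equal to the detectable effect. A bias of that size is enough to have produced its significance.

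**3. One omitted covariate, no true effect.** Let m be the arm difference in the covariate (SD), g its correlation with 3-month FAC, and r its correlation with baseline FAC. If baseline FAC differs between arms only through the covariate (by r × m), the bias of the two-term model is m × (g − ρr). The values of m, g and r are all assumptions.

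| m, g | Bias, r = 0 | Rejection, n = 50 | n = 30 | Bias, r = 0.3 | Rejection, n = 50 | n = 30 |
|---|---|---|---|---|---|---|
| 0.3, 0.2 | 0.06 | 6.6% | 5.9% | 0.3 × 0.02 = 0.006 | 5.0% | 5.0% |
| 0.5, 0.3 | 0.15 | 15.3% | 11.0% | 0.5 × 0.12 = 0.06 | 6.6% | 5.9% |
| 0.5, 0.4 | 0.20 | 23.6% | 15.9% | 0.5 × 0.22 = 0.11 | 10.5% | 8.2% |

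Rejection is two-sided at 5%, from the noncentral t with noncentrality bias/SE. A simulation with 4,000 replicates per cell agrees: 6.4/15.4/23.7% and 5.8/11.1/15.5% for r = 0; 5.0/6.9/9.9% and 4.8/6.0/8.7% for r = 0.3. With the covariate in the model, rejection was 4.8-5.5%. That is true by construction, because the only confounder is then measured.

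**4. Price of four extra covariates if none is prognostic.** With N = 2n children, the SE ratio to the two-term model is about √((N − 3)/(N − 7)):
- 50 per arm: √(97/93) = 1.02
- 30 per arm: √(57/53) = 1.04
- 20 per arm: √(37/33) = 1.06
- 10 per arm: √(17/13) = 1.14 (simulated 1.15)

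Adding six sites (Section 1.4 judges the study "feasible within a 5-7 site clinical trial"), with assumed Arm A shares of 30-70% per site, gives simulated ratios of 1.09, 1.135, 1.20 and about 1.55. Site terms are therefore costly at early looks.

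**The case against.** **The estimate is already adjusted.** Baseline FAC is a named covariate and probably among the strongest predictors of later FAC. A reader might infer that the primary estimate is unadjusted; the text of Section 7.4.3 rules that out. What stands is narrower: nothing beyond baseline FAC is in the model.

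**Other safeguards exist.** Both arms share clinical eligibility criteria (Section 3.1) and the screen at the end of surgery (Section 4.3). The core laboratory is blinded (Appendix B), and hospital-adjusted models are planned (Section 7.4.6). These help. But shared criteria do not balance children within the eligible range, blinded reading protects measurement only, and the hospital models cover centre alone and are not primary. The interaction models address effect modification, not confounding.

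**Family choice may matter little.** Section 1.4 reports that few eligible families with a product declined, so a reader who takes parental choice to be the main source of controls goes beyond the text. The route with the clearer link to prognosis is failed collection after early delivery.

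**Every bias size is assumed.** This is correct. With modest correlation between the omitted covariate and baseline FAC, the inflation ranges from none to about 10%.

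**Phase IIb only.** The Introduction leaves definitive proof to later studies. That lowers the weight of the point but does not change what the primary p-value can support.

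**Conclusion.** The concern holds as a gap in model specification. Assignment depends on product availability, collection success and family choice. The primary ANCOVA and its 12-month counterpart adjust for baseline FAC only, and no analysis addresses unmeasured confounding.

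A reader might infer that the trial will favour the cells, or that its false-positive rate is 24%. The documents support neither. They report no imbalance between arms and no direction, and a bias could work against the cells. The ranges of 7-24% (50 per arm) and 6-16% (30 per arm) rest on an assumed correlation of 0.6, an omitted covariate unrelated to baseline FAC, and assumed biases of 0.06 to 0.20 SD. With a covariate correlated 0.3 with baseline FAC, the range is about 5-10%. The firmer guide is the tipping point: at correlation 0.6, a bias of about 0.14 SD (50 per arm) or 0.17 SD (30 per arm) could by itself account for the significance of an estimate equal to the 80%-power effect.

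The plan should be changed, though the exact covariate list is a matter of judgement. Confidence is medium, because the need follows from the text but the size of the problem does not.

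**What to change.** In Section 7.4.3, and by reference for 12-month FAC in Section 7.4.4:

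1. Pre-specify the primary ANCOVA as arm, baseline FAC, age and weight at Stage II, diagnosis (HLHS versus variant) and baseline NT-proBNP. A single propensity score built from the same baseline variables would also serve.
2. State a rule for missing baseline covariates, such as single imputation that ignores arm. The last-observation rule in Section 7.3 has no earlier planned value to carry forward here.
3. Use this same model at every interim and at the final analysis, so that one model governs any declaration under Section 7.4.2.
4. Keep the two-term model and the hospital-adjusted model of Section 7.4.6 as sensitivity analyses.
5. Add gestational age, where the medical record holds it, as a sensitivity covariate, because of the early-delivery route in Section 1.4.
6. Add a tipping-point analysis for unmeasured confounding, since measured covariates cannot be relied on to remove confounding by family choice.

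**Cost.** This is mainly SAP wording. Weight and NT-proBNP are baseline items in Section 6.1.1, and age and diagnosis are needed for eligibility (Section 4.1.1). The HLHS or variant label is not a separate item in Section 6.1.1, so the sponsor should confirm that it is recorded. If none of the four covariates is prognostic, the SE rises about 2% at 50 per arm, 4% at 30, 6% at 20 and 15% at 10. At correlation 0.6, the detectable effect moves from 0.453 to about 0.46 SD at 50 per arm (0.453 × 1.02) and from 0.589 to about 0.61 SD at 30 (0.589 × 1.04). If the covariates are prognostic, the loss is smaller or becomes a gain.
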